6.3 Diet/Activity/Other Considerations

6.3.1 Diet

Subjects should maintain a normal diet unless modifications are required to manage an AE such as diarrhea, nausea or vomiting. They will be instructed to avoid Seville orange, star fruit, grapefruit and their juices.

6.3.2 Contraception

Everolimus and/or itacitinib may have adverse effects on a fetus in utero. Furthermore, it is not known if everolimus and/or itacitinib have transient adverse effects on the composition of sperm. Therefore while enrolled, all subjects must agree not to participate in a conception process (i.e. active attempt to become pregnant or to impregnate, sperm donation, in vitro fertilization, etc.).

Female subjects of reproductive potential (women who have reached menarche or women who have not been post-menopausal for at least 24 consecutive months, i.e., who have had menses within the preceding 24 months, or have not undergone a sterilization procedure [hysterectomy or bilateral oophorectomy]) must have a negative serum or urine pregnancy test performed within 72 hours of Cycle 1/Day 1 per Table 9 Schedule of Study Procedures.

All participants participating in sexual activity that could lead to pregnancy must agree to use two methods of birth control. The two birth control methods can be either two barrier methods or a barrier method plus a hormonal method to prevent pregnancy. Subjects should start using birth control from screening throughout the study period up to 120 days after the last dose of study therapy.

The following are considered adequate barrier methods of contraception: diaphragm with spermicide (cannot be used in combination with cervical cap), cervical cap with spermicide (only if you have not given birth), male condom or female condom, contraceptive sponge (only if you have not given birth). Hormonal contraceptives (estrogen/progestin pill or progestin-only pill), contraceptive skin patch, vaginal contraceptive ring, or subcutaneous contraceptive injection. Intrauterine Device (IUD), surgical sterility (tubal ligation or a partner that has undergone a vasectomy), or contraceptive rod implanted into the skin is also considered an acceptable method of birth control as long as a barrier method is also utilized.

Subjects may also agree to agree to completely abstain from intercourse during participation in this study and for 120 days after your last dose of study drug. Abstinence at certain times of the cycle only, such as during the days of ovulation, after ovulation and withdrawal are not acceptable methods of birth control.

Subjects should be informed that taking the study medication may involve unknown risks to the fetus (unborn baby) if pregnancy were to occur during the study. In order to participate in the study they must adhere to the contraception requirement above. If there is any question that a subject will not reliably comply with the requirements for contraception, that subject should not be entered into the study.

Varion 11.0

6.3.3 Use in Nursing Women

It is unknown whether the study drugs are excreted in human milk. Since many drugs are excreted in human milk, and because of the potential for serious adverse reactions in the nursing infant, subjects who are breast-feeding are not eligible for enrollment.

Page 44 of 72

6.4 Study Intervention Phase

6.4.1 Cycle 1 Day 1

- Physical Examination and evaluation of ECOG PS (Appendix 13.3)
- Vital signs: blood pressure, heart rate, temperature, weight, oxygen saturation
- Baseline QOL FACT-lym questionnaire (Appendix 13.1; does not need to be repeated if done within 14 days prior to starting therapy)
- CBC with WBC differential and platelets (does not need to be repeated if previously performed within 3 days of starting treatment with itacitinib and everolimus)
- Serum Chemistry panel including sodium, potassium, chloride, CO₂, calcium, serum creatinine, BUN, total bilirubin, alkaline phosphatase, AST, ALT, uric acid, LDH, and erythrocyte sedimentation rate (does not need to be repeated if previously performed within 3 days of starting treatment with itacitinib and everolimus)
- For women of childbearing potential, a serum pregnancy test must be performed within 72 hours prior to initiating treatment with itacitinib and everolimus unless the subject is actively undergoing egg harvesting (including HCG injections)

6.4.2 Cycle 1 Day 8 (+/- 3 Days)

- Physical Examination and evaluation of ECOG PS (Appendix 13.3)
- Vital signs: blood pressure, heart rate, temperature, weight, oxygen saturation
- CBC with differential and platelets (does not need to be repeated if previously performed within 24 hours before Day 8 Visit)
- Serum Chemistry panel including sodium, potassium, chloride, CO₂, calcium, serum creatinine, BUN, total bilirubin, alkaline phosphatase, AST, ALT, uric acid, and LDH (does not need to be repeated if previously performed within 24 hours before Day 8 Visit)
- Review of interim adverse events and concomitant medications

Note: Only CBC and CMP results must be received before the subject can proceed with mediation treatment. Other test results may be received after the subject has received mediation treatment.

Version 11.0

Page 45 of 72

6.4.3 Cycle 1 Day 15 (+/- 3 Days)

- Physical Examination and evaluation of ECOG PS (Appendix 13.3)
- Vital signs: blood pressure, heart rate, temperature, weight, oxygen saturation
- CBC with differential and platelets (does not need to be repeated if previously performed within 24 hours before Day 15 Visit)
- Serum Chemistry panel including sodium, potassium, chloride, CO₂, calcium, serum creatinine, BUN, total bilirubin, alkaline phosphatase, AST, ALT (does not need to be repeated if previously performed 24 hours before Day 15 Visit)
- Review of interim adverse events and concomitant medications
- QOL FACT-lym questionnaire (Appendix 13.1)

Note: Only CBC and CMP results must be received before the subject can proceed with mediation treatment. Other test results may be received after the subject has received mediation treatment.

6.4.4 Cycle 1 Day 22 (+/- 3 days)

- CBC with differential and platelets (does not need to be repeated if previously performed within 24 hours before Day 22 Visit)
- Serum Chemistry panel including sodium, potassium, chloride, CO₂, calcium, serum creatinine, BUN, total bilirubin, alkaline phosphatase, AST, ALT (does not need to be repeated if previously performed 24 hours before Day 22 Visit)

6.4.5 Cycles 2-24 Day 1 (+/- 7 days)

- Physical Examination and evaluation of ECOG PS (Appendix 13.3)
- Vital signs: blood pressure, heart rate, temperature, weight, and oxygen saturation
- CBC with differential and platelets (does not need to be repeated if previously performed within 24 hours before Day 1 Visit)
- Serum Chemistry panel including sodium, potassium, chloride, CO₂, calcium, serum creatinine, BUN, total bilirubin, alkaline phosphatase, AST, ALT, uric acid, LDH, and erythrocyte sedimentation rate (does not need to be repeated if previously performed 24 hours before Day 1 Visit)
- Review of interim adverse events and concomitant medications
- Fasting lipid profile every 2 months during active therapy (triglycerides, total cholesterol, HDL and LDL) starting with Day 1 of Cycle 2.
- QOL FACT-lym questionnaire (Appendix 13.1)

Version 11.0 Page 46 of 72

Note: Only CBC and CMP results must be received before the subject can proceed with mediation treatment. Other test results may be received after the subject has received mediation treatment.

Additional cycles of investigational treatment may be added if in the opinion of the investigator that the benefit risk ratio for the subject continues to be favorable. During these additional cycles, the same assessments will be captured as cycles 4-24.

In the event that a telemedicine visit is conducted, the following tests will be postponed until the next in-person visit:

- Physical examination
- Vital Signs
- Return of IP
- Fact-lym QOL questionnaire

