4.7 Telemedicine Visits

To safeguard the welfare of subjects during COVID surges and/or situations that may negatively impact their safety, telemedicine visits may be utilized. The telemedicine option will be discussed with the subject prior to the scheduled visit. Visit documentation will state that the visit was conducted via telemedicine, and it will state which intervention(s) and/or assessment(s) were and were not completed. If clinically indicated, labs may be performed at an outside testing facility.

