- In disease follow-up phase subjects who discontinue study treatment for a reason other than disease progression will be followed-up for 2 years from EOT. They should be assessed at least every 3 months (+/- 1 month) using physical exam and standard of care blood work during the first year and every 6 months (+/- 1 month) for the second year. Imaging will be done every 6 months (+/- 1 month) during the 2 years of follow-up.
- g Plus/minus 3 days
- h Plus/minus 7 days
- Viral screening tests to include testing for Hepatitis B (hepatitis B core antibody, hepatitis B surface antigen, hepatitis B surface antibody). Hepatitis C (hepatitis C antibody), HIV (HIV 1 and 2 antibody or viral load)
- Does not need to be repeated if done within 14 days prior starting study treatment
- k PCP prophylaxis (see appendix 13.6 for options) will start before or at Day 1 Cycle 1 and continue until EOT visit.
- EOT visit should occur within 28 days of last dosing.
- m Results may be obtained up to 3 days prior to treatment.
- ⁿ CBC and CMP results must be received before the subject can proceed with mediation treatment.
- ^o Antiviral medication to be taken for the duration of the active trial treatment
- P Additional cycles of investigational treatment may be added if in the opinion of the investigator that the benefit risk ratio for the subject continues to be favorable.
- Not performed when visit is via telemedicine. If clinically indicated, labs may be performed at an outside testing facility.
- r Study medicine will be shipped directly to subject when a telemedicine visit occurs.

Version 11.0 Page 53 of 72

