13 APPENDIX

FACT-Lym Questionnaire 13.1

Below is a list of statements that other people with your illness have said are important. Please circle or mark one number per line to indicate your response as it applies to the past 7 days.

	PHYSICAL WELL-BEING	Not at all	A little bit	Some- what	Quite a bit	Very much
GP1	I have a lack of energy	0	1	2	3	4
GP2	I have nausea	0	1	2	3	4
GP3	Because of my physical condition, I have trouble meeting the needs of my family	0	1	2	3	4
GP4	I have pain	0	1	2	3	4
GP5	I am bothered by side effects of treatment	0	1	2	3	4
GP6	I feel ill	0	1	2	3	4
GP7	I am forced to spend time in bed	0	1	2	3	4
	SOCIAL/FAMILY WELL-BEING	Not at all	A little bit	Some- what	Quite a bit	Very much
GS1	I feel close to my friends	0	1	2	3	4
GS2	I get emotional support from my family	0	1	2	3	4
GS3	I get support from my friends	0	1	2	3	4
GS4	My family has accepted my illness	0	1	2	3	4
GS5	I am satisfied with family communication about my illness	0	1	2	3	4
GS6	I feel close to my partner (or the person who is my main support).	0	1	2	3	4
Q1	Regardless of your current level of sexual activity, please answer the following question. If you prefer not to answer it, please mark this box and go to the next section.					
GS7	I am satisfied with my sex life	0	1	2	3	4

Itacitinib + everolimus in HL
Version 11.0
Page 66 of 72

Please circle or mark one number per line to indicate your response as it applies to the past 7 days.

	EMOTIONAL WELL-BEING	Not at all	A little bit	Some- what	Quite a bit	Very much
GE1	I feel sad	0	1	2	3	4
GE2	I am satisfied with how I am coping with my illness	0	1	2	3	4
GE3	I am losing hope in the fight against my illness	0	1	2	3	4
GE4	I feel nervous	0	1	2	3	4
GE5	I worry about dying	0	1	2	3	4
GE6	I worry that my condition will get worse	0	1	2	3	4
	FUNCTIONAL WELL-BEING	Not at all	A little bit	Some- what	Quite a bit	Very much
GF1	FUNCTIONAL WELL-BEING I am able to work (include work at home)				_	
GF1		all	bit	what	bit	much
	I am able to work (include work at home)	all 0	bit 1	what	bit 3	much 4
GF2	I am able to work (include work at home)	all 0	bit 1 1	what 2 2	bit 3 3	much 4
GF2 GF3	I am able to work (include work at home)	0 0 0	bit 1 1	2 2 2	bit 3 3	4 4 4
GF2 GF3 GF4	I am able to work (include work at home)	0 0 0 0	bit 1 1 1 1	what 2 2 2 2	bit 3 3 3 3	4 4 4 4

Version 11.0 Page 67 of 72

Please circle or mark one number per line to indicate your response as it applies to the past 7 days.

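### FACT-Lym is put off or skipped at telemedicine visits although the subject could complete it at home, so exploratory quality-of-life forms are lost needlessly

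*Combined protocol and SAP*

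**What the plan says.** FACT-Lym is scheduled at Cycle 1 Day 1 (Section 6.4.1), Cycle 1 Day 15 (6.4.3), Day 1 of each of Cycles 2 to 24 (6.4.5) and the end-of-treatment visit (6.4.6). A baseline form from the 14 days before treatment is accepted.

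Section 4.7 allows remote visits: "To safeguard the welfare of subjects during COVID surges and/or situations that may negatively impact their safety, telemedicine visits may be utilized". It gives no limit and no expected frequency. For Cycles 2 to 24, Section 6.4.5 then states: "In the event that a telemedicine visit is conducted, the following tests will be postponed until the next in-person visit". The list has four entries: physical examination, vital signs, return of investigational product, and "Fact-lym QOL questionnaire". In Table 9 the FACT-Lym cell for Cycles 2 to 24 carries footnote q, which reads: "Not performed when visit is via telemedicine". Footnote r adds: "Study medicine will be shipped directly to subject when a telemedicine visit occurs".

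The form in Appendix 13.1 is addressed to the subject, who is asked to mark one number per line "to indicate your response as it applies to the past 7 days". No section describes a way to complete it away from the clinic.

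Quality of life is an exploratory objective in both phases (2.1.3, 2.2.3) and an exploratory endpoint (3.3.1.3, 3.3.2.3). Section 7.6 describes the questionnaire but sets no time point, change score, model or missing-data rule for it.

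**The concern.** The other three entries on the postponed list need the subject, or the returned tablets, to be at the clinic. FACT-Lym does not: the subject reads it and marks it. Grouping it with them gives up a measurement that the remote visit does not prevent.

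Postponing looks like a way to keep the form, but each later cycle visit already has its own FACT-Lym, and the 7-day recall ties a score to the week in which it is completed. What is at stake is how completely the exploratory quality-of-life course is observed on treatment. FACT-Lym is the only quality-of-life instrument named, and Section 7.6 has no rule for missing scores. With up to 28 subjects enrolled, scores at later cycles will be few in any case.

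**Working it through.** The plan states no figure for quality-of-life completeness, so there is none to reproduce. The check is a comparison of timings and then a count.

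**Does a postponed form recover the missed score?**

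- Inputs: 28-day cycles (Study Summary), a Day 1 window of +/- 7 days (6.4.5), and a 7-day recall (Appendix 13.1).
- Call the planned Day 1 of the missed cycle day 0. Its window closes at day +7.
- The next cycle's Day 1 is planned for day +28, and its window opens at 28 - 7 = day +21.
- A form completed at the earliest permitted next visit covers days +14 to +21. A form completed as late as allowed for the missed visit covers days 0 to +7. The two periods do not overlap.
- The next visit's own FACT-Lym covers the same days as the postponed one, so the postponed form adds no information.

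A form put off to the next cycle visit is therefore a lost score. If several visits in a row are remote, the next in-person visit yields one usable form for all of them.

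**How many forms are exposed?**

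For a subject treated for c cycles:

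- scheduled forms = 1 (Cycle 1 Day 1) + 1 (Cycle 1 Day 15) + (c - 1) + 1 (end of treatment) = c + 2
- exposed forms = c - 1, because the rule applies from Cycle 2 and footnote q is not on the end-of-treatment cell

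With c = 24, 26 forms are scheduled and 23 are exposed (23/26 = 88%). With c = 6, 8 are scheduled and 5 are exposed.

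**How many are lost?**

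Let f be the share of Cycle 2 onward visits held by telemedicine. The documents do not give f, so the values below are assumptions that show a range. Share lost = f(c - 1)/(c + 2).

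| f (assumed) | 24 cycles: forms lost of 26 | Share | 6 cycles: forms lost of 8 | Share |
|---|---|---|---|---|
| 10% | 2.3 | 9% | 0.5 | 6% |
| 25% | 5.75 | 22% | 1.25 | 16% |
| 50% | 11.5 | 44% | 2.5 | 31% |

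These figures take every form due at a remote visit as lost. If the form were completed remotely inside the window, the rule would cost no forms at any value of f.

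**The case against.** The strongest reply concerns weight. Quality of life is exploratory, with no hypothesis, model or decision attached, and no endpoint of higher rank uses FACT-Lym. Telemedicine is conditional, its frequency is unknown, and nothing in the documents supports a rate as high as 50%. Adverse-event review is not on the postponed list, and Section 3.3 has staff record B symptoms and pruritus at study visits, so some symptom information remains. All of this stands, and it limits the point to a minor improvement.

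A second reply is that completing forms only in the clinic keeps a single mode of administration. That is a legitimate aim, but sending the same paper form with the drug keeps the subject marking the same page. Mixed modes arise only if telephone or email is used. It is also true that no section says how the form is administered. That the subject completes it is read from the form's own instruction.

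A third reply is that an unscheduled visit (Section 6.8) could bring the subject in before the window closes, so not every postponed form is certain to be lost. This is possible, but Section 6.4.5 does not call for such a visit.

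Two stronger readings are tempting. A reader might infer that less well subjects are moved to telemedicine, so that the missing scores bias the quality-of-life course. Section 4.7 does not say so. It refers to COVID surges and to situations that may affect safety, which supports possible clustering in calendar time but shows no link to how a subject feels. A reader might also see a flat contradiction between the text and the table. The two can be read together, as not done at that visit and done at the next one in person, although the wording should still be aligned.

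**Conclusion.** The point holds as a minor one. The telemedicine rule gives up exploratory quality-of-life data that could be collected, because a form put off to the next cycle visit cannot stand for the missed one.

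The exposure is firm: 23 of 26 scheduled forms for a subject completing 24 cycles. The loss is not known. At assumed telemedicine rates of 10%, 25% and 50% it is about 9%, 22% and 44% of that subject's forms, and 6%, 16% and 31% for a subject treated for 6 cycles. These figures assume that each form due at a remote visit is lost, and they rest on rates that the documents do not give.

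Missing forms may cluster in calendar time. No direction or size of bias can be shown. The complete response rate, the secondary endpoints, the sample size and the stopping rules are untouched by how FACT-Lym is handled.

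**What to change.** Remove FACT-Lym from the postponed list in Section 6.4.5 and footnote q from the FACT-Lym cell in Table 9. State that at a telemedicine visit the subject completes the form remotely within the +/- 7 day window, preferably on the same paper form enclosed with the shipped drug, and that the mode of completion is recorded. The other cells that carry footnote q are outside this change.

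The cost is a sheet of paper in a parcel that is already being sent, and arrangements for its return. No visit or procedure is added. The downside is possible mixed modes if some forms are taken by telephone or email, which is why paper is preferred. A statistical adjustment for mode is not needed: Section 7.6 has no quality-of-life model to hold it, and with at most 28 subjects a mode effect could not usefully be estimated.

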6.4.6 End of Treatment Visit (EOT)

The following will be performed at the time of study discontinuation, whether due to study completion or early withdrawal from study participation. This visit should occur within 28 days from the last dosing:

- Physical Exam and evaluation of ECOG PS (Appendix 13.3)
- Vital signs (Blood pressure, heart rate, temperature, weight, oxygen saturation)
- CBC with differential and platelets
- Serum chemistry panel including sodium, potassium, chloride, CO₂, calcium, serum creatinine, BUN, total bilirubin, alkaline phosphatase, AST, ALT, uric acid, LDH, and erythrocyte sedimentation rate
- Fasting lipid profile
- Serum pregnancy test (women of child-bearing potential)
- Assessment of adverse events and concomitant medications
- QOL FACT-lym questionnaire (Appendix 13.1)

6.4.7 Safety Assessments

The safety follow-up period is the interval between the EOT visit and the scheduled follow-up visit, which should occur 28 days (+/- 7 days) after the EOT visit (or after the last dose of study drug if the EOT visit was not performed). Adverse events and SAEs must be reported as

Itacitinib + everolimus in HL
Version 11.0
Page 47 of 72

described in section 8.3. Reasonable effort should be made to have the subject return for the follow-up visit and report any AEs that may occur during this phase.

If a subject is scheduled to begin a new anticancer therapy before the end of the safety follow-up period, the safety follow-up visit should be performed before new anticancer therapy is started. Once new anticancer therapy has been initiated, the subject will move into the survival follow-up period.

6.4.8 Follow-up Phase

6.4.8.1 Follow-up Period for Disease Status

Subjects who discontinue study treatment for a reason other than disease progression will move into the disease status follow-up period for 2 years from the EOT visit. They should be assessed at least every 3 months (+/- 30 Days) using physical exam and standard of care blood work (CBC with diff, Serum Chemistry panel including sodium, potassium, chloride, CO₂, calcium, serum creatinine, BUN, total bilirubin, alkaline phosphatase, AST, ALT,) during the first year and every 6 months (+/- 30 Days) for the second year. The follow-up portion of the study will end at 2 years from the EOT of the last subject or earlier once all subjects have discontinued study treatment, and all subjects have died, have withdrawn consent, or are lost to follow-up.

The imaging frequency will be at the discretion of the treating physician, but at least every 6 months (+/- 1 month) to monitor disease status during the first 2 years after EOT. Every effort should be made to collect information regarding disease status until:

- The start of new antineoplastic therapy
- Disease progression
- Death
- The end of the study

Patients who undergo HDT/allogeneic SCT within one year of completing study treatment will be followed for one year after the transplant, in order to collect data from the following events: GVHD, pulmonary complications, hepatic veno-occlusive disease, immune-mediated AEs, critical illness, and transplant-related mortality.

6.4.8.2 Follow-up for Survival Status

Once a subject has confirmed disease progression, or starts a new anticancer therapy, the subject moves into the survival follow-up period. The subject should then be contacted by telephone, email, visit, or by review of the subject's EMR at least every 12 weeks, according to the tables below, to assess for survival status. Subject will remain enrolled until completion of follow-up, death, withdrawal of consent, or the end of the study, whichever occurs first.

Version 11.0 Page 48 of 72

Disease Follow-Up Phase (for subjects with non-disease progression)

	EOT + 28 days	EOT + 3 mo.	EOT + 6 mo.	EOT + 9 mo.	EOT +12 mo.	EOT + 18 mo.	EOT + 24 mo.
Physical		X	X	X	X	X	X
Labs*		X	X	X	X	X	X
All AEs**	X						
Imaging			X		X	X	X

^{*} CBC with diff, serum chemistry panel including sodium, potassium, chloride, CO2, calcium serum creatinine, BUN, total bilirubin, alkaline phosphatase, AST, ALT

Survival Follow-Up Phase (for subjects with disease progression or those who have started a

new anticancer therapy)

	EOT* + 28 days	EOT + 12 wks.	EOT + 24 wks.	EOT + 36 wks.	EOT + 48 wks.**
All AEs***	X				
Check survival****		X	X	X	X

^{*} Survival Follow-Up starts at EOT if PD, or if not PD, then when a new anticancer therapy starts

